7.4 Safety Monitoring

The IPPI program does not entail risks to the NH resident or staff member. Each involved individual can refuse to participate at any time. The IPPI program is based on a preferred activity leading to a meaningful and enjoyable use of time between the resident and care partner.

The NIA IMPACT Collaboratory Safety Officer will oversee all data and safety monitoring activities for this study to evaluate the progress of the study, and to review procedures for maintaining the confidentiality of data, the quality of data collection, management, and analyses. Advarra IRB will conduct the ethical review required for the protection of human subjects.

In addition, all activities for this intervention will abide by expected Centers for Medicare and Medicaid Services Health and Safety care requirements within the NHs.

8 INTERVENTION DISCONTINUATION

Participating in the IPPI intervention is optional for residents. Residents can refuse participation at any time. The staff can choose to discontinue the IPPI with any participant based upon their clinical judgement and the individual may be withdrawn from the study.

Withdrawal can also follow a significant health change or hospitalization that makes the participant unable to continue to participate in the IPPI intervention activities. Implementation team clinical staff will make a judgement call.

Participants may also be withdrawn due to death. Residents living with dementia in a NH are a vulnerable population, health events are common and anticipated (i.e. falls).

Participants may also be withdrawn from the study if the individual leaves the NH to move to another NH. The resident must continue to reside in the same NH for the 6-months of the study period to be engaged in the intervention.

For all reasons of withdrawal, the implementation team for a given resident will communicate the withdrawal to the PI with the second to last column on the Resident Preferences Worksheet stating the date and the reason.

While there is no formal plan for replacement of subjects, due the rolling nature of enrollment, additional eligible residents may be added to the study to accommodate a withdrawal if it occurs within the first 3 consecutive months of the study.

9 STATISTICAL CONSIDERATIONS

9.1 General Design Issues

The primary objective is to effectively deploy the IPPI program so that care providers can use the program as a part of their routine care delivery. We hypothesize that implementation will result in decreased expressions of behavioral distress and/or depressive symptoms for residents engaged in the program at 3-month and 6-month intervention follow-up and increased knowledge of emotion-focused communication and self-efficacy for using emotion-focused communication for care providers.

Our secondary objective is to demonstrate program feasibility and fidelity as well as document barriers and facilitators in implementation.

For this pilot study, we will have a non-randomized, within-person design, examining how individual levels of distress change from baseline to 3-months to 6-months. We will report rates of overall sample change versus stability. No randomization will occur for this trial, as the primary purpose is to establish pragmatic feasibility of the intervention.

The primary clinical outcome will be reports of distress as rated in the residents' MDS 3.0 annual or quarterly assessments in Section E and Section D (Saliba & Buchanan, 2009). These items will also be rated by the implementation team care partner delivering the intervention. These data will be collected at baseline (to determine eligibility) and at 3-months and 6-months post-intervention enrollment. The items in Section D and Section E are validated standardized items used to assess all NH residents in the United States receiving funding from the Centers for Medicare and Medicaid Services. Section D depression item responses are drawn from the widely used and validated PHQ-9 (Kroenke et al., 2001; anhedonia, sad mood, poor self-esteem, poor appetite, or restlessness). The items ask *“Over the past 2 weeks, have you been bothered by any of the following problems?”* and then if the resident responds “yes” they are asked *“About how often have you been bothered by this?”*. Item level scores are 0 (*did not occur*), 1 (2-6 days), 2 (7-11 days), or 3 (12-14 days). The Section E behavior items have been used as a valid indicator of behavioral distress (Saliba & Buchanan, 2009). Items include the presence of verbal, physical or other behavior symptoms directed toward others, rejection of care, and wandering. For section E, each behavior is rated with a 0 (*did not occur in the past week*), 1 (*occurred 1-3 days in the past week*), 2 (*occurred 4-6 days*) or 3 (*occurred daily*). For each resident care partners will have designated a targeted mood or behavior item selected for improvement and assessed via MDS data. The targeted mood or behavior selected by the care partner at baseline will be reassessed at 3-months and 6-months and recorded as 0 = *stayed the same as baseline* (e.g., score on MDS 3.0 baseline assessment equals score on MDS 3.0 follow-up assessment), 1 = *got better* (e.g., score on

MDS 3.0 baseline assessment is better (lower) than the score on the MDS 3.0 follow-up assessment), or 2 = *got worse* (e.g., score on MDS 3.0 baseline assessment is worse (higher) than the score on MDS 3.0 follow-up assessment) for our primary, person-centered clinical outcome. The type of mood or behavior item being tracked will be different for each resident (e.g., wandering for one, verbal behavior for another)

The secondary clinical outcomes will be knowledge and self-efficacy pre-and post-EFCT data for all implementation team members. To assess knowledge gained from the content of the intervention, participants will respond to 16 intervention specific multiple-choice or multiple-response items prior to training (pre-test) and upon completion of the training (post-test). Items were created to specifically check learning on all key course elements. Items assess knowledge regarding ways to recognize and respond to emotions (e.g., anger, pleasure). A total count of correct answers is computed (possible range: 0 to 27; note, total exceeds 16 as some questions required more than one correct response to be selected). For self-efficacy, consistent with Bandura's (1997) initial conception of self-efficacy that it is behavior-specific, we created items modeled after Fortinsky and colleagues' (2002) and Steffen and colleagues' (2002) work with caregivers, that were tailored to the specific intervention content presented in the EFCT. By using a tailored set of items created specifically for this course, the impact of the specific intervention activities can be tested. The scale includes 9-items asking participants how confident on a scale of 0 (not at all confident) to 10 (certain you can do it) they are completing the proposed activity. Items assess confidence in identifying one's own feelings, ability to respond effectively to those emotions, identifying emotions in others, and responding effectively to their emotions. A mean-item total score is computed (possible range: 0 to 90) and internal consistency ratings are high ($\alpha = .90$).

To assess feasibility and fidelity as a component of our second objective, we will track the number of residents each NH is able to engage in the program via data collected from the Resident Preferences Worksheet. This worksheet also tracks alignment of important preferences with activities; we will review for appropriateness. We will track how many implementation team members complete the EFCT based on data from the EFCT LMS. We will also provide a standardized Pragmatic Checklist that site champion(s) will use to observe an IPPI session by each care partner to establish implementation fidelity. This short checklist incorporates learning from the online trainings into a Yes/No format to ensure that good communication practices are utilized. Each checklist item is equal to one point and a total number of points will be calculated to assess the fidelity to the intervention process. Each care partner delivering the IPPI will be observed once with each resident by an implementation team member. Care partners will record the date and how long the IPPI session lasted in the EMR. This documentation will be used to report on the amount, frequency, and duration of IPPI delivery to determine if the recommended 2 sessions per week over the course of 6 months were implemented. Further, participant responsiveness to the IPPI protocol will be measured through the question "*Would you like to do this activity again?*" posed to residents upon completion of an IPPI activity and recorded in the EMR. Finally, acceptability, feasibility, and appropriateness will be calculated by staff in both the EFCT post-test and the exit interview (Weiner et al., 2017; AIM, IAM, and FIM measures). Qualitative data will be collected to determine facilitators and barriers in the Exit interview with participating implementation team members.

9.2 Sample Size and Randomization

Nine NHs will be invited to participate in this pragmatic implementation feasibility study. Care partners will initiate implementation of the preferred IPPI activity with 3-7 residents per month upon completion of their quarterly or annual MDS 3.0 assessment (this will serve as baseline data) in each NH. Initiation of engagement will be rolling, adding an estimated 3-8 residents per month for 3-4 consecutive months. This study will include between 105-1110 residents and between 30-75 staff members from the implementation teams. Findings from this study will guide any needed adaptions to the implementation, approach, and power needed for a full-scale Stage IV effectiveness ePCT study.

9.2.1 Treatment Assignment Procedures

For this pragmatic implementation feasibility study, subjects will not be randomized. Individuals will be enrolled in any of the 7 NHs per the proposed eligibility/enrollment plan.

9.3 Interim analyses and Stopping Rules

No interim analyses are planned since the study is mostly focused on the feasibility of implementing the IPPI program. However, the study PI will monitor indicators of project feasibility and fidelity and offer virtual coaching as required to ensure implementation is being completed (i.e., ensure an implementation team is set up, ensure training with the EFCT and the IPPI are completed).

While not anticipated, in the event of repeat SAE/AEs linked with the study protocols, a safety review will be conducted by the PI in concert with the assigned Safety Officer to determine whether study efforts should be discontinued. We will submit an interim and final Data Safety Monitoring (DSM) submitted for review by the IMPACT NIA Safety Officer.

9.4 Outcomes

Outcomes data will be analyzed descriptively.

9.4.1 Primary outcome

The primary clinical outcome will be reports of distress as rated in the residents' MDS 3.0 annual or quarterly assessments in Section E and Section D (Saliba & Buchanan, 2009). These items will also be rated by the implementation team care partner delivering the intervention. These data will be collected at baseline (to determine eligibility) and at 3-months and 6-months post-intervention enrollment. For each resident, a targeted mood or behavior item selected for improvement and assessed via MDS data will be used as the primary outcome. The targeted mood or behavior will be recorded as 0 = *stayed the same as baseline* (e.g., score on MDS 3.0 baseline assessment equals score on MDS 3.0 follow-up assessment), 1 = *got better* (e.g., score on MDS 3.0 baseline assessment is better (lower) than the score on the MDS 3.0 follow-up assessment), or 2 = *got worse* (e.g., score on MDS 3.0 baseline assessment is worse (higher) than the score on MDS 3.0 follow-up assessment) for our primary, person-centered clinical outcome at 3-months and 6-months post

intervention enrollment. The type of mood or behavior item being tracked will be different for each resident (e.g., wandering for one, verbal behavior for another).

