provided IPPI activity training videos (each 10-15 min), and be provided the IPPI manual with a checklist of steps, 60+ different IPPI protocols that address all 16 MDS 3.0 preferences in Section F, sample letters/scripts introducing the IPPI to family and staff, and communication tips sheets. Any member of the implementation team can deliver an IPPI activity. We will ask champion(s) to demonstrate an IPPI for care partners (e.g., CNAs) to watch, and then observe each care partner's initial IPPI implementation.

The champion(s) will be provided with a pragmatic data collection binder of paper forms (See Appendix A) to record these initial observations (in the form of a checklist). In addition, this binder will include a form to document staff training completion, resident preferences, and the behavior or mood item to target with the IPPI program that is most distressing to each identified eligible resident. Forms for champion(s) to document adverse events and withdraws will also be included in the binder.

Implementation team members will align stated preferences of each eligible resident with specific IPPI protocols (i.e., important preference for reading will be matched with a reading activity IPPI protocol). While any implementation team member can deliver an IPPI activity, we will encourage care partners to take the lead in implementation of the preferred IPPI activity with each enrolled resident on a regular basis. Initiation of engagement will be rolling, adding 3-7 residents per month for 3-4 consecutive months. The care partners will implement a minimum of 2 IPPI protocols per week with each resident for 6 months, to ensure continuous completion of the intervention through to the date of the resident's next two quarterly or annual MDS 3.0 assessment (3-month and 6-month follow-up data). The project manager will provide virtual coaching to communities throughout implementation as needed. Table 1 below outlines the intervention structure and implementation strategy. In addition, we identify the implementation measure/metric we will track during the course of implementation.

Table 1. IPPI Intervention Structure, Implementation Strategy, and Implementation Measures

Intervention Structure	Implementation Strategy	Implementation Measure
Establish Co-champions	Assess Organizational Readiness	Organizational Readiness for Implementing Change (ORIC) ³⁰

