4 SELECTION AND ENROLLMENT OF PARTICIPANTS

The IPPI intervention targets distress of PLWD. As a result, champion(s) will be trained to identify residents in each of the participating nine communities that have both cognitive impairment (Brief Inventory for Mental Status (BIMS) score of 0-12) and who have recently triggered for distress as reported in Section D (non-zero response on PHQ-9 items of anhedonia, sad mood, poor self-esteem, poor appetite, or restlessness) or Section E (non-zero response on a behavior) in the MDS 3.0.

Inclusion Criteria

Participants of any age, race, gender, or ethnicity will be eligible for enrollment if the following criteria are met:

- The individual is a long-stay resident in one of the nine participating UCH NH locations partnering with the PI for this project.
- The most recent MDS 3.0 assessment indicates a BIMS score of 0-12 *and* a non-zero response on PHQ-9 items of anhedonia, sad mood, poor self-esteem, poor appetite, or restlessness or Section E behavior item(s).

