6.2.3 Follow-up Visits

- IPPI completions 2x weekly:
 - The Fidelity Assessment with Pragmatic Checklist will be completed the first time a member of the intervention team completes an IPPI with a resident. This will be completed by the site champion when shadowing the care partner in implementation.
 - IPPIs will be documented in the UCH EMR through Point-Click-Care.
 - During implementation, troubleshooting (count of contacts of the implementation teams with the PI/Project team) will be recorded.
 - If an eligible resident is withdrawn from participation, the withdrawal date, and the reason will be documented on an Intervention Withdrawal form and provided to the project PI. This form is part of the binder that will be provided to each site champion(s).
 - Adverse Events will be reported directly to the PI if they occur as per section 7.3 below.
- 3-months (~90 days):
 - Distress data (Section E and Section D) from the next completed MDS 3.0 assessment (annual or quarterly) will be provided to the PI by the UCH IT Corporate office. The Centers for Medicare and Medicaid Services require completion of an assessment every 3-months; however, experience indicates that there is individual variability in actual completion times and therefore we will not enforce a strict allowable time window for these data. Change in each Section E/Section D item will be scored as 0 = *stayed the same as baseline* (e.g., score on MDS 3.0 baseline assessment equals score on MDS 3.0 follow-up assessment), 1 = *got better* (e.g., score on MDS 3.0 baseline assessment is better (lower) than the score on the MDS 3.0 follow-up assessment), or 2 = *got worse* (e.g., score on MDS 3.0 baseline assessment is worse (higher) than the score on MDS 3.0 follow-up assessment) for our primary, person-centered clinical outcome.
- 6-months (~180 days):
 - Distress data (Section E and Section D) from the next completed MDS 3.0 assessment (annual or quarterly ~6-months post baseline assessment) will be provided to the PI by the UCH IT Corporate office. The Centers for Medicare and Medicaid Services require completion of an assessment every 3-months; however, experience indicates that there is individual variability in actual completion times and therefore will not enforce a

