***email address will be used to identify if individual completed the Emotion Focused Communication Training**

IPPI Program – Resident Preferences Worksheet

Site champion(s) will maintain a password protected list of the name of each resident that is enrolled into the IPPI program along with a unique ID# that is determined by the champion(s). This password protected file will be shared with the PI who will then link the data from this worksheet to the electronic medical record data prior to deidentifying.

After completing a resident's preference assessment, identify and record their most important preferences in the column "Important Preferences." Next, review the list of IPPI protocols then record the protocols that match the resident's important preferences in the "Matching IPPIs" column. Review the list of matching IPPIs with the implementation team member(s) that will be facilitating the activity with the resident and let them chose which IPPI activities (1-2) they are most comfortable doing. After they've chosen the IPPI activities, record their selection in the "IPPIs Selected" column. Identify one or more resident behaviors that are the target outcome for the intervention as indicated on the MDS Section E. Finally, note if the resident completed the project and if there were any adverse events.

Resident Unique ID#	Important Preferences	Matching IPPIs	IPPIs Selected by implementation team	Supplies Needed Location	Which targeted behavior(s) do you hope the IPPI will remediate? Check all that apply	Did the resident complete the IPPI Project? Yes No If no, why did the individual not complete the project?	Did the resident have any adverse events? Yes No If Yes, complete Serious Adverse Event Report Form
	•	•	•	○	 Physical behavioral symptom  Verbal behavioral symptom  Other behavioral symptom  Rejection of Care  Wandering  Depressive Mood Symptoms	○	○

Observation Checklist of Fidelity to IPPI Protocol conducted by Champion

Did the person delivering the IPPI do any of the following?

1. Yes No N/A Introduce self to resident
2. Yes No N/A Introduce IPPI activity to resident
3. Yes No N/A Consider possible distractions (background noise, visual/tactile)
4. Yes No N/A Check that individual could hear or was wearing hearing aids if applicable
5. Yes No N/A Interrupt resident in the middle of a visit (reverse coded)

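### The primary resident outcome is defined in two conflicting ways, and the worksheet that records the target cannot deliver the single-item version

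*Combined protocol and SAP*

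**What the plan says.** **Statistical sections.** Section 9.4.1 (Primary outcome) states that "a targeted mood or behavior item selected for improvement and assessed via MDS data will be used as the primary outcome". Section 9.1 (General Design Issues) agrees: "For each resident care partners will have designated a targeted mood or behavior item selected for improvement and assessed via MDS data". Section 9.5 (Data Analyses) codes change for each resident's targeted behaviors, in the plural, and reports the percentages improved, unchanged and worsened.

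**Procedures.** Section 6.2.3 (Follow-up Visits) says for the 3-month assessment: "Change in each Section E/Section D item will be scored as 0", followed by the codes for better and worse. It labels the result the primary, person-centered clinical outcome. The 6-month paragraph does the same for the items of the two sections. Neither paragraph mentions the target.

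**Choice of target.** Section 3 (Study Design) says that the binder records "the behavior or mood item to target with the IPPI program that is most distressing to each identified eligible resident". In Appendix A, the Resident Preferences Worksheet instructs staff: "Identify one or more resident behaviors that are the target outcome for the intervention as indicated on the MDS Section E". Its tick list has five behaviors and one mood entry, "Depressive Mood Symptoms", under the direction "Check all that apply".

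**Eligibility.** Section 4 requires a BIMS score of 0-12 and a non-zero response on any one of five Section D mood items or on a Section E behavior. Section 9.1 scores every item from 0 to 3.

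**The concern.** The improved/unchanged/worsened split is the only resident clinical result that 9.5 plans, and 9.1 provides no control group against which a distorted split would show. Section 9.2 says that the findings will guide the full-scale trial. If two sections name different quantities as primary, the reported percentages depend on which section the analyst follows.

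Even if 9.4.1 is followed, the form does not reliably supply one scorable MDS item per resident. The target may be several items, or a mood box that matches no single item, or possibly an item that scored 0 at baseline. An item at 0 has only one direction in which to move, so its result reflects the scale as well as the resident.

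**Working it through.** The plan states no power, alpha or effect size for this outcome (9.4 says that outcomes are analyzed descriptively), so there is no planned figure to reproduce. The check compares definitions and the codes that each allows.

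**1. Items in play.** Section D contributes 5 items (Table 1; section 4). Section E contributes 5: verbal, physical and other behavioral symptoms, rejection of care, and wandering (9.1). Total: 5 + 5 = 10.

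**2. Effect of the two definitions.** Take a resident who enters on exactly one non-zero item, the minimum that section 4 requires, and read better as a fall in score.

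- Scoring every item (6.2.3): at most 1/10 = 10% of items can improve, and 9 of 10 cannot.
- Scoring the targeted item (9.4.1), if it is the non-zero one: 1/1 = 100% can improve.

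The documents give no baseline distribution, so this contrast describes the minimally eligible resident and not a typical one.

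**3. Codes available by baseline score.** All follow-up scores 0-3 were enumerated. In 6.2.3, 9.1 and 9.4.1 the bracketed explanation of *got better* describes a baseline lower than follow-up, and that of *got worse* a baseline higher than follow-up. Both run against their labels.

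| Baseline | Plain meaning | Brackets as printed |
|---|---|---|
| 0 | same, worse | same, better |
| 1 or 2 | same, better, worse | same, better, worse |
| 3 | same, better | same, worse |

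An item at 0 is one-sided either way, and the side depends on which reading is applied.

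**4. What the worksheet delivers.**

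- *Entry on mood alone.* Every Section E item may be 0. The instruction line names only Section E, while the tick list below it offers mood. The two do not agree.
- *Mood box ticked.* The box could stand for any of five Section D items. If the resident entered on sad mood only, 4 of those 5 are at 0, and no rule says which one to score.
- *Several boxes ticked.* If one target improves and another worsens, 9.4.1 has no rule for placing the resident in one category.

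**5. Ceiling if some targets are at 0.** Let f be the share of residents whose scored target was 0 at baseline, and p the true share improving among the rest. On the plain meaning, the maximum percent improved is 1 − f and the reported rate is p × (1 − f). Neither f nor p is in the documents. The values below are assumptions, applied to the 105 to 110 residents in the Précis.

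| f (assumed) | Residents (105 × f to 110 × f) | Ceiling | Reported rate if p = 50% (assumed) |
|---|---|---|---|
| 5% | 5.25 to 5.5 | 95% | 47.5% |
| 10% | 10.5 to 11 | 90% | 45% |
| 20% | 21 to 22 | 80% | 40% |
| 30% | 31.5 to 33 | 70% | 35% |

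**The case against.** The best defense is that the plan evidently intends a present symptom. The target is the most distressing item, it is selected for improvement, and the worksheet asks for something indicated on the MDS. Nothing tells staff to pick an absent symptom. This stands as a reading of intent, but it is not a check. Staff judgment can differ from an MDS score that looks back one week (Section E) or two weeks (Section D). The reviews in 6.2.2 compare activities with preferences and look for the target in the care plan; neither compares the target with its baseline score.

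A reader might go further and infer that the worksheet forces residents who entered on mood onto a behavior scored 0. The documents do not support this. A resident with no Section E behavior has none indicated there, and the mood box is available. What remains is an instruction line that contradicts its own tick list.

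A reader might also infer that some residents can only be coded as unchanged or worse. That holds on the plain meaning only. As printed, a rise from 0 is coded as better.

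Nor is all-item scoring the settled rule: 9.1, 9.4.1 and 9.5 all point to the target. It is a conflict to reconcile.

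It is fair to add that the outcome is descriptive, with no test or threshold to distort, and that nothing in the documents shows f to be above zero.

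**Conclusion.** The point holds as a contradiction in the primary outcome together with a form that cannot supply the single item which 9.4.1 requires. Both follow from the text without any assumption. For a minimally eligible resident, the two definitions differ by a factor of ten in the share of scored items able to improve (10% against 100%).

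The missing baseline condition is secondary. Taken alone it would be close to a missing detail; it matters because the form leaves room for a target at 0 and the scoring is then one-sided. Its size cannot be determined from the documents. The ceiling of 1 − f assumes the plain meaning of better and worse, and the tabulated values of f and p are illustrations. The documents do not support a claim that the results will be biased by a known amount, or in a known direction. The plan should be corrected on this point; the correction does not call the pilot design into question.

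**What to change.** - **6.2.3:** at both time points, score the targeted item only. Report change in the other Section D and E items in a separate descriptive table.
- **9.1 and 9.4.1:** state that the target is one named MDS item scored above 0 on the resident's baseline assessment.
- **Worksheet (Appendix A):** reword the instruction to refer to a non-zero score on MDS Section D or Section E, list the five mood items separately, and have staff mark one primary target.
- **9.5:** list separately any resident whose target was 0 at baseline.
- **6.2.3, 9.1 and 9.4.1:** correct the direction of the bracketed explanations of better and worse in the same edit.

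The cost is wording in four sections and a revision of one paper form. The separate line in 9.5 uses baseline MDS data that the study already collects. There are two downsides. Staff could not name as target a symptom absent on the baseline MDS. Choosing items that are elevated at baseline also favors regression toward improvement in this uncontrolled design, and that should be stated wherever the percentages are reported.

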1 STUDY OBJECTIVES

1.1 Primary Objective

The primary objective is to effectively deploy the IPPI program so that care providers can use the program as a part of their routine care delivery. We hypothesize that implementation of IPPI will result in decreased expressions of behavioral distress and/or depressive symptoms for residents engaged in the program at 3-months and 6-months following intervention initiation and increased knowledge of emotion-focused communication and self-efficacy for using emotion-focused communication for care providers delivering the intervention.

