9.5 Data Analyses

Analysis of data will be descriptive. To address our first objective of clinical impact for residents, we will code a change score for each enrolled resident's targeted behaviors (e.g., improved, stayed same, worsened) in two ways. We will use the MDS 3.0 data between baseline and 6 months. We will report aggregate percentages of improved, stayed same, and worsened from the MDS 3.0 data. For implementation team members, the outcomes of knowledge and self-efficacy will be analyzed through paired samples t-tests of pre- and post-EFCT test measures.

For our second objective of feasibility and fidelity, we will calculate the number of residents each NH is able to engage as a percentage of the goal (e.g., 15 residents minimum) via data collected from the Resident Preferences Worksheet. We will also calculate the percentage of the implementation team that completed the EFCT based on data from the EFCT LMS. Finally, we will calculate the average number of IPPIs completed (via the EMR). Acceptability, feasibility, and appropriateness will be calculated according to responses from the exit interview (Weiner et al., 2017; AIM, IAM, and FIM measures). Qualitative data collected by the semi-structured exit interview

will be audio recorded, transcribed verbatim, and coded for facilitators and barriers in Dedoose.

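### The scoring rule for the primary resident outcome is written backwards in all four places: a rise in distress is scored as got better and a fall as got worse

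*Combined protocol and SAP*

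**What the plan says.** The primary clinical outcome is the change from baseline in one targeted mood or behavior item per resident, taken from MDS 3.0 Section D or Section E. Section 9.4.1 gives three codes. Code 0 is no change from baseline. The other two are "1 = *got better* (e.g., score on MDS 3.0 baseline assessment is better (lower) than the score on the MDS 3.0 follow-up assessment" and "2 = *got worse* (e.g., score on MDS 3.0 baseline assessment is worse (higher) than the score on MDS 3.0 follow-up assessment".

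The same comparison appears in 6.2.3 for the 3-month and again for the 6-month assessment ("score on MDS 3.0 baseline assessment is better (lower) than the score on the MDS 3.0 follow-up assessment"), and in 9.1 ("MDS 3.0 baseline assessment is better (lower) than the score on the MDS 3.0 follow-up assessment").

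Section 9.1 also fixes the direction of the scales. For Section D: "Item level scores are 0 (*did not occur*), 1 (2-6 days), 2 (7-11 days), or 3 (12-14 days". For Section E: "each behavior is rated with a 0 (*did not occur in the past week*), 1 (*occurred 1-3 days in the past week", rising to 3 for daily occurrence.

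Section 1.1 hypothesizes that "implementation of IPPI will result in decreased expressions of behavioral distress and/or depressive symptoms for residents engaged in the program". Section 9.5 describes the analysis with labels only: "We will report aggregate percentages of improved, stayed same, and worsened from the MDS 3.0 data".

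**The concern.** On both scales a lower score is better. A resident has improved when the follow-up score is below the baseline score. The text makes baseline the subject of the comparison: *got better* is tied to a baseline lower than follow-up, and *got worse* to a baseline higher than follow-up. The words in brackets (lower for better, higher for worse) describe the scale correctly. They are attached to the wrong visit.

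These parentheses are the only place where scores are mapped to categories, and the percentages in 9.5 are the only directional result specified for resident distress. Section 9.5 plans no mean change, model or test for residents that would expose a reversal. A programmer who checks one section against another finds the same rule each time. Under 9.2 the findings are meant to guide a full-scale effectiveness study, so the sign of this result matters beyond the pilot.

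**Working it through.** **Inputs**
- Item scale 0 to 3 for Sections D and E, higher meaning more frequent distress (9.1).
- Rule as written (6.2.3 twice, 9.1, 9.4.1): code 1 if baseline < follow-up; code 2 if baseline > follow-up; code 0 if equal.
- Rule that fits the labels and the hypothesis in 1.1: code 1 if follow-up < baseline; code 2 if follow-up > baseline; code 0 if equal.
- n = 108 residents (Précis, Design and Outcomes), used only for illustration.

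The plan gives no figure to reproduce here, so the check enumerates the possible score pairs.

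**Step 1. Single cases**

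| Baseline to follow-up | Distress | As written | Label-consistent |
|---|---|---|---|
| 3 to 0 | gone | 2, got worse | 1, got better |
| 1 to 3 | rose | 1, got better | 2, got worse |
| 2 to 2 | unchanged | 0, same | 0, same |

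**Step 2. Full grid.** There are 4 × 4 = 16 pairs: 4 ties, 6 falls and 6 rises. The two rules agree on the 4 ties and disagree on all 6 + 6 = 12 changes.

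**Step 3. Targeted item non-zero at baseline (assumption).** There are 3 × 4 = 12 pairs: 3 ties, 6 falls and 3 rises. The rules disagree on all 6 + 3 = 9 changes. As written, the grid gives 3 better, 3 same and 6 worse; the label-consistent rule gives 6, 3 and 3. Every full resolution to 0 is scored *got worse*. A resident who starts at 3 can never be scored *got better*, because no follow-up score exceeds 3.

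**Step 4. Effect on the reported result.** Let I and W be the true numbers improved and worsened among n residents. Under the rule as written, reported improved = W/n and reported worsened = I/n. The net result (I − W)/n becomes (W − I)/n. The percentage unchanged is not affected.

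**Step 5. Illustration at n = 108.** The splits are assumed; the documents give none.

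| True improved / same / worsened | True improved, worsened | Reported improved, worsened | Net, true and reported (points) |
|---|---|---|---|
| 27 / 54 / 27 | 25.0%, 25.0% | 25.0%, 25.0% | 0 and 0 |
| 32 / 54 / 22 | 29.6%, 20.4% | 20.4%, 29.6% | +9.3 and −9.3 |
| 54 / 38 / 16 | 50.0%, 14.8% | 14.8%, 50.0% | +35.2 and −35.2 |

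The net values are (32 − 22)/108 = 9.3 and (54 − 16)/108 = 35.2 points.

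**The case against.** The best defense is that the labels are the definition and the parentheses are only examples, since each is introduced by *e.g.* The scales, the hypothesis and the wording of 9.5 all point one way, so an analyst would probably follow the labels. Literal coding would also be conspicuous, because every resident whose symptom disappeared would appear as worse. The analysis is descriptive, the main purpose is feasibility, and no resident-level test, sample size or stopping rule depends on the code.

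Much of this stands. The intent is clear, the harm is conditional, and the documents do not show how the data were coded. The harm can also be undone, because 6.2.1 has the baseline and both follow-up assessments supplied. Other resident results are planned and are unaffected: change versus stability (9.1), and engagement and delivery counts (9.4.2 and 9.5). The grid counts are score pairs, not residents. They assume a single 0–3 item per resident, whereas the worksheet in Appendix A allows several targets and offers one general box for depressive mood. The splits also assume that all 108 residents are evaluable, although section 8 foresees withdrawal and death.

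None of this supplies a correct statement of the rule. The *stayed the same* parenthesis has the same form and plainly works as a scoring rule, so the other two will be read in the same way.

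**Conclusion.** The concern holds. The comparison that defines improvement and worsening in the primary clinical outcome is reversed in all four places, and no section corrects it. If it is programmed as written, every changed score is misclassified, the percentages improved and worsened are exchanged exactly, and the net result changes sign. The size of the error equals the true difference between the two percentages: zero if they are equal, and 35.2 points in either direction in the largest assumed example. That the two percentages exchange follows from the text alone; the example sizes rest on the assumed splits. Whether the error reached the data cannot be told from the documents. Even if the coding was right, a reader of the protocol cannot confirm the direction of the reported result.

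**What to change.** In 6.2.3 (3 months and 6 months), 9.1 and 9.4.1, put follow-up first: *got better* means a follow-up score lower than baseline, and *got worse* means a follow-up score higher than baseline. State the same direction once in 9.5, where the percentages are specified. The codes 0, 1 and 2 can stay, since only percentages are planned.

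Before any percentage is reported, cross-tabulate the coded category against the raw change in score and check the analysis code. Assign this by name of role to the principal investigator or the statistical consultant, who hold the data (6.2.1 and 10.2); under 7.1 the biostatistician who directs the analysis has no direct access to them.

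The cost is four wording corrections, one added sentence and one table. No new data are needed.
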